#### Hematologic Improvement (HI)

Improvements must last at least 2 months in the absence of ongoing cytotoxic therapy. When protocol therapy requires the initiation of further treatment before the 2 month period, patients can be included in the response criteria into which they fit at the time therapy is restarted.

Hematologic improvement should be described by the number of individual, positively affected cell lines (eg, HI-E; HI-E + HI-N; HI-E + HI-P + HI-N)

Hematologic Improvement response categories include the following:

• Erythroid response (HI-E)

For patients with pretreatment hemoglobin less than 11g/dL:

- Hemoglobin increase by > 1.5 g/dL
- Relevant reduction of units of RBC transfusions by an absolute number of at least 4 RBC/8wk compared with the pretreatment transfusion number in the pervious 8 wk. (\*)
- (\*) Only RBC transfusions given for Hgb < 9.0 g/dL will count in the RBC transfusion response evaluation.
- Platelet response (HI-P)

For patients with a pretreatment platelet count  $< 100 \times 10^{9}$ /L:

An absolute increase of  $\geq$  30 x 10 $^{9}$ /L or more for patients starting with > 20 x 10 $^{9}$ /L platelets

An increase from  $< 20 \times 10^9$ /L to  $> 20 \times 10^9$ /L, and by at least 100%.

Neutrophil response (HI-N)

For patients with pretreatment neutrophil count <  $1.0 \times 10^9$ /L: At least a 100% increase and an absolute increase >  $0.5 \times 10^9$ /L.

#### Progression/relapse after HI

One or more of the following:

- A 50% or greater decrement from maximum response levels in granulocytes or platelets
- A reduction in hemoglobin concentration by at least 1.5 g/dL
- Transfusion dependence (in the absence of other explanation, such as hemolysis, hemorrhage, etc).

#### 13.0 CRITERIA FOR REMOVAL FROM STUDY

Patients may withdraw from the study at any time. Patients who discontinue from the study will be encouraged to return to the study site to undergo the evaluations listed for the End of Treatment Visit.

At the discretion of the Investigator, the investigator may remove a patient from the study for the following reasons:

- Due to disease progression
- Noncompliance with study procedures
- Need of treatment with medications not allowed by the study protocol
- Patient no longer consents to participate in the study
- Intercurrent illness that interferes with study assessments
- Incidence or severity of AEs in this study indicates a potential health hazard to the patient
- For the third occurrence of the same Grade ≥3 non-hematological toxicity
- For the third episode of clinically significant bleeding or fourth episode of complicated febrile neutropenia
- Investigator discretion
- Other treatments become available which are more appropriate for the individual patient

To the extent possible, patients must strictly follow the standard dosing schedule. Patients who miss 3 doses or more (out of 4 doses) in a cycle in the absence of study drug related toxicity will be discontinued.

If the reason for withdrawal is the occurrence of an AE, the patient will be followed by the Investigator until such events resolve, stabilize, and according to the Investigator's judgment there is no need of further follow-up. The reason for withdrawal from the study will be documented in the case report form.

#### 14.1 BIOSTATISTICS

#### Primary endpoint evaluation

The primary endpoint of this study is to investigate the efficacy of Selinexor in patients with MDS refractory to hypomethylating agents (decitabine and/or 5-azacytidine). The standard treatment in this setting is supportive care, where the response rate is assumed to be zero. Therefore, in this population, a response rate of 25% would be considered promising, whereas a 5% response rate would not be considered promising. For purposes of assessing the primary endpoint, response categories will include CR, PR, marrow CR (mCR), or Hematologic Improvement. Using a Simon's two-stage minimax design, this trial will accrue a maximum of 20 patients. Early termination may occur if no responses are observed in the first 13 patients. If at least one response is observed, the trial will continue to the maximum sample size. At the end of the trial, the treatment strategy will be considered promising in this patient population if at least 3 patients achieve a response. The type I and type II errors are set at 0.10.

The response evaluation cohort will include those patients who have completed at least 3 of 4 planned doses of their first cycle of therapy and have undergone at least one full scheduled post-treatment disease assessment (informative bone marrow aspirate or biopsy, cytogenetics, and CBC with differential). For patients who come off study after completing at least 3 of 4 planned doses of their first cycle of therapy and are unable to undergo (or refuse) a bone marrow procedure, an assessment for Hematologic Improvement (based on CBC data) will be performed and described and an attempt will be made to obtain follow-up CBC data for the 8 weeks mandated to confirm Hematologic Improvement according to the MDS International Working Group response criteria. Patients who come off study after starting study drug because of toxicity, death, or withdrawal of consent prior to undergoing a response assessment will not be replaced and will be considered a treatment failure. Patients who enroll on study but do not receive study therapy will be replaced.

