Efficacy Assessment	Efficacy will be assessed by evaluation of bone marrow as pirates and biopsies, complete blood counts, and transfusion records. Hematologic Improvement will be assessed continuously, with the use of CBC values and transfusion records. At the time of bone marrow aspirates and biopsies, full efficacy evaluations will be performed, taking into account blood and bone marrow parameters, and responses will be assessed using the 2006 Modified MDS International Working Group Response Criteria.
Safety Variables & Analysis:	The safety and tolerability of Selinexor and ST will be evaluated by means of drug related AE reports, physical examinations, and laboratory safety evaluations. Common Terminology Criteria for Adverse Events (CTCAE) V4.03 will be used for grading of AEs. Investigators will provide their assessment of causality as 1) unrelated, 2) possibly related, or 3) probably or definitely related for all AEs.
Statistical Analysis:	Primary endpoint evaluation
	The primary endpoint of this study is to investigate the efficacy of Selinexor in patients with MDS refractory to hypomethylating agents (decitabine and/or 5-azacytidine). The standard treatment in this setting is supportive care, where the response rate is assumed to be zero. Therefore, in this population, a response rate of 25% would be considered promising, whereas a 5% response rate would not be considered promising. For purposes of assessing the primary endpoint, response categories will include CR, PR, marrow CR (mCR), or Hematologic Improvement. Using a Simon's two-stage minimax design, this trial will accrue a maximum of 20 patients who receive study drug. Early termination may occur if no responses are observed in the first 13 patients. If at least one response is observed, the trial will continue to the maximum sample size. At the end of the trial, the treatment strategy will be considered promising in this patient population if at least 3 patients achieve a response. The type I and type II errors are set at 0.10.  The response evaluation cohort will include those patients who have completed one cycle of therapy and have undergone at least one full scheduled post-treatment disease assessment (informative bone marrow aspirate or biopsy, cytogenetics, and

Memorial Sloan Kettering Cancer Center IRB Number: 14-005 A(17)

Approval date: 25-Jan-2021

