#### 12.0 CRITERIA FOR THERAPEUTIC RESPONSE/OUTCOME ASSESSMENT

The primary and secondary efficacy endpoints of this study will be assessed using the 2006 Modified MDS International Working Group response criteria (Cheson et al., 2006).

Patients will be eligible for the primary efficacy endpoint if they have undergone at least one cycle of therapy, and are evaluable for response. Patients will be evaluable for Hematologic Improvement with the availability of CBC parameters and transfusion records, and will be evaluable for all response categories if they undergo at least one bone marrow procedure (first planned marrow for response assessments is after dosing is completed for the first 21-day cycle).

For the primary endpoint, overall CR, marrow CR, and PR, and HI responses will be tabulated.

According to the 2006 Modified MDS International Working Group response criteria, response categories include the following:

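### The population for the primary response rate is defined in three different ways, and some treated patients have no assigned outcome, so the denominator is not fixed.

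*Combined protocol and SAP*

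**What the plan says.** Three places set the entry rule for the primary response analysis.

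- **Section 1.0, Synopsis, Statistical Analysis:** "The response evaluation cohort will include those patients who have completed one cycle of therapy", together with a full scheduled disease assessment after that cycle. The same text describes accrual this way: "this trial will accrue a maximum of 20 patients who receive study drug".
- **Section 12.0:** "Patients will be eligible for the primary efficacy endpoint if they have undergone at least one cycle of therapy, and are evaluable for response". It adds "Patients will be evaluable for Hematologic Improvement with the availability of CBC parameters and transfusion records", asks for a marrow before all response categories can be assessed, and states "For the primary endpoint, overall CR, marrow CR, and PR, and HI responses will be tabulated".
- **Section 14.1, Primary endpoint evaluation:** "The response evaluation cohort will include those patients who have completed at least 3 of 4 planned doses of their first cycle of therapy", plus a full assessment (informative marrow, cytogenetics, blood count). For patients who come off study after those doses without a marrow, "an assessment for Hematologic Improvement (based on CBC data) will be performed and described". Accrual and the interim look read "this trial will accrue a maximum of 20 patients. Early termination may occur if no responses are observed in the first 13 patients", without the synopsis's reference to receipt of study drug.

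The synopsis, Section 9.1.1 and Section 14.1 share one failure clause. Patients who leave after starting drug because of toxicity, death or withdrawn consent, before a response assessment, are failures and are not replaced. Only enrolled patients who never receive drug are replaced.

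Among the secondary analyses, Section 14 names an at-least-one-dose set for safety and an exact 95% confidence interval for the response rate in therapy-related MDS. It gives neither for the primary response rate.

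**The concern.** The three definitions can admit different patients, and none of them closes the denominator. Read literally, two kinds of treated patient are outside the Section 14 cohort, are not named as failures and are not replaced:

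- **(a)** patients who leave before assessment for a Section 13 reason other than toxicity, death or withdrawn consent: non-compliance, missed doses without drug toxicity, intercurrent illness, a disallowed or more suitable treatment, or investigator discretion;
- **(b)** patients who take two or fewer cycle 1 doses and stay on study, even if they later respond.

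Two things are at stake. If the cohort is the reported denominator and those left out are non-responders, the reported rate is too high. If a responder falls outside the cohort, or HI without a marrow is described but not counted, the trial loses power and may miss its threshold of three.

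**Working it through.** **1. The plan's own design reproduces.** Inputs from Section 14.1: unpromising rate 5%, promising rate 25%, 13 patients in stage 1, 20 in total, stop on 0 responses in 13, promising on at least 3 responses, error limits 0.10 each.

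P(promising | p) = Σ over x ≥ 1 of P[Bin(13, p) = x] × P[Bin(7, p) ≥ 3 − x]

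- p = 0.05: 0.3512 × 0.0444 (x = 1) + 0.1109 × 0.3017 (x = 2) + 0.0245 (x ≥ 3) = 0.0156 + 0.0335 + 0.0245 = **0.0736**.
- p = 0.25: 0.1029 × 0.5551 + 0.2059 × 0.8665 + 0.6674 = 0.0571 + 0.1784 + 0.6674 = **0.903**.

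An exhaustive search confirms that 20 is the smallest total meeting both limits, with 13, 0 and 3 as stated. The sample size is not in question.

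**2. Who is left over.** The text was checked for each group.

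- *Group (a).* The Section 10 footnotes schedule an End of Study marrow for patients leaving for reasons other than progression. Section 10.2 asks only for all efforts to obtain it, and Section 13 only encourages patients to return, so an assessment is not assured.
- *Group (b).* Section 9.2.6 skips a dose missed by more than 24 hours. Two such doses leave 2 of 4, below the Section 14 threshold. Section 13 discontinues for missed doses only at 3 of 4, and only without drug toxicity. The patient has not come off study, so the failure clause does not apply.
- *Progressors.* These are largely covered by the Section 12 failure category and the marrow scheduled at progression.
- *Named failures.* They have no response assessment, so the cohort definition excludes them while the failure clause counts them. Section 14 is therefore inconsistent within itself.

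**3. Effect on the reported rate.** The documents give no number of excluded patients; 1 to 4 of 20 is an assumption. With 3 responders, rate = 3/N and the interval is Clopper-Pearson:

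| Denominator | Rate | Exact 95% CI |
|---|---|---|
| 20 | 15.0% | 3.2–37.9% |
| 19 | 15.8% | 3.4–39.6% |
| 18 | 16.7% | 3.6–41.4% |
| 17 | 17.6% | 3.8–43.4% |
| 16 | 18.8% | 4.0–45.6% |

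**4. Effect on power.** Suppose a fraction q of responders is not counted (assumed). The effective rate is 0.25 × (1 − q), entered in the formula of step 1:

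| q | Effective rate | Power |
|---|---|---|
| 0 | 0.2500 | 0.903 |
| 0.05 | 0.2375 | 0.880 |
| 0.10 | 0.2250 | 0.854 |
| 0.20 | 0.2000 | 0.786 |

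**5. How often one patient decides the result.** At p = 0.25, P(exactly 3 in 20 with at least 1 in the first 13) = P[Bin(20, 0.25) = 3] − 0.75^13 × P[Bin(7, 0.25) = 3] = 0.1339 − 0.0041 = **0.130**. As a share of promising results this is 0.130 / 0.903 = 14%. In those trials one uncounted responder leaves 2, and the conclusion reverses.

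**The case against.** The best reply is that the intent is clear enough. The synopsis sets the maximum at 20 patients who receive drug, only never-treated patients are replaced, and the commonest early losses count as failures. Together these suggest 20 treated patients, with the first 13 of them forming stage 1. Three of four doses could be the working meaning of a completed cycle. For HI, the sentence in Section 14 goes on to seek eight weeks of follow-up counts to confirm the improvement, which would have little purpose if it could not count. The decision rule is a count of responders, so dropping a non-responder cannot change it. The number of patients affected is unknown.

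Much of this stands as evidence of intent and as a limit on size. It does not close the gap. The synopsis wording concerns accrual and is followed at once by a narrower response cohort; Section 14 omits it. No section equates three doses with a completed cycle, and Sections 12 and 14 would still differ on whether a marrow is needed. No section says that confirmed HI without a marrow counts towards the three responses, or what happens to a responder who took two cycle 1 doses. A patient in group (a) usually has no documented response to lose, so the risk to the decision comes mainly from group (b) and from HI without a marrow.

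It is also fair that patients were already enrolled under earlier amendments, so a change of analysis set in this open-label trial should be dated and justified.

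**Conclusion.** The concern holds, and the plan should be corrected. Sections 1, 12 and 14 give different entry rules, and no text makes all treated patients the denominator or says who the first 13 are. The design is correct, and type I error is not inflated with 20 treated.

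Both harms are conditional. The first requires that the Section 14 cohort is used as the reported denominator and that those left out are non-responders. The second requires that a documented response is disregarded under a literal reading. The sizes in steps 3 and 4 rest on assumed counts: the shift in the rate is modest against the width of the exact interval, and the loss of power matters because the planned value is only just above 0.90. The correction cannot recover power lost because patients cannot be assessed; it makes every documented response count and fixes the denominator.

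**What to change.** Use one primary analysis set in Sections 1, 12 and 14: all patients who receive at least one dose of selinexor, the set Section 14 already uses for safety.

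- Apply it to the interim look (first 13 treated), the final rule of at least 3 responses, and the reported rate with its exact 95% confidence interval (20 patients if the trial goes to full size).
- Count any treated patient without a documented CR, PR, marrow CR or HI, for whatever reason, as a non-responder. This replaces the three-reason failure clause in the synopsis, Section 9.1.1 and Section 14.1.
- State, in line with Section 12, that HI confirmed from blood counts and transfusion records under the IWG criteria counts as a response without a marrow.
- Keep the cohort with at least 3 of 4 doses and a full assessment as a sensitivity analysis.
- Date and justify the change in the amendment.

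The cost is wording. The sample size, the interim look and the three-responder threshold do not change. The reported rate may be slightly less favourable.

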#### Analysis of secondary endpoints

- 1. Response duration will be caluated among patients who achieve a response of HI, mCR, PR or CR using Kaplan-Meier methodology. Median duration of response and the corresponding 95% confidence interval will be estimated.
- 2. The frequency of stable disease will be tabulated and exact 95% confidence intervals will be estimated.
- 3. The response rate and response duration will also be described for the generally poor-risk therapy-related MDS patients enrolled on this study (therapy-related MDS accruals may approach ~ 50%, as seen in MSKCC protocol 06-054). The response rate will be estimated along with an exact 95% confidence interval to evaluate the proportion of patients who have

- CR, PR, mCR or Hl. Median response duration and corresponding 95% confidence intervals will be estimated.
- Overall survival from the time of study enrollment will be caluated using Kaplan-Meier methodology. Overall survival curves will be displayed for the study population along with selected quantiles and corresponding 95% confidence intervals of survival.
- 5. Since Selinexor may require chronic dosing to maintain its effect, the overall tolerability and safety of chronic Selinexor dosing will be described on patients throughout all cycles of treatment who have received at least 1 dose of selinexor. Tolerability will be assessed by calculating the proportion of patients who withdraw consent due to chronic low-grade (1/2) toxicity. Safety will be calculated by determining the proportion of patients who have any toxicity listed in section 11.0. This will be calculated overall at each treatment cycle and separately by the Selinexor dose received at the time of the selected toxicity. Proportions and exact 95% confidence intervals will be calculated.
- Descriptive statistics will be used to explore the relationship between the results of the
  pharmacodynamics studies and therapeutic response or study entry disease parameters.
  The Wilcoxon rank-sum statistic or Fisher's exact test may be used to assess these
  associations.

Accrual rates and study duration

It is expected that the study will accrue 1-2 patients per month, resulting in completion of accrual in 10-20 months.

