## 9.2 Dosing Adjustments

Toxicity will be graded according to NCI CTCAE, version 4.03; the therapy modifications described below are applied according to this severity grading.

If more than one different type of toxicity occurs concurrently, the most severe grade will determine the modification.

Re-escalation of the study drug is allowed as outlined in the sections that apply for the specific toxicity. If drug-related toxicity requires a treatment delay of more than 21 days the patient is taken off protocol treatment.

Each dose modification or treatment delay must be documented, including the respective reason.

Based on observations from the ongoing Phase 1 studies in patients with advanced hematological and solid tumors, we note that selinexor shows a reasonably wide therapeutic range, with activities from ~10mg/m2 to ≥50mg/m2. Therefore, in order to optimize specific anti-tumor activity and the

patient's tolerability, we will allow for dose and/or schedule modifications as described below. Patients should also be treated aggressively with supportive care to reduce toxicities.

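### Section 14.1 item 5 measures tolerability only by consent withdrawal for chronic grade 1/2 toxicity, so other toxicity stops and dose reductions go uncounted and worsening toxicity can lower the figure

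*Combined protocol and SAP*

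**What the plan says.** Tolerability of chronic selinexor dosing is a stated secondary objective. Section 14.1, item 5 of the secondary analyses, applies to patients who received at least one dose and defines the measure in one sentence: "Tolerability will be assessed by calculating the proportion of patients who withdraw consent due to chronic low-grade (1/2) toxicity". The next sentence defines safety separately: "Safety will be calculated by determining the proportion of patients who have any toxicity listed in section 11.0". The safety proportion is reported by treatment cycle and by the dose being taken when the toxicity occurred. Exact 95% intervals are planned.

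Other sections provide for leaving treatment because of toxicity without withdrawing consent:

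- Section 9.2: "If drug-related toxicity requires a treatment delay of more than 21 days the patient is taken off protocol treatment".
- Section 13.0 lets the investigator remove a patient on several toxicity grounds. One is general: "Incidence or severity of AEs in this study indicates a potential health hazard to the patient". Another concerns a severe event that keeps coming back: "For the third occurrence of the same Grade ≥3 non-hematological toxicity". A further one covers repeated blood-related complications: "For the third episode of clinically significant bleeding or fourth episode of complicated febrile neutropenia". Loss of consent is a separate entry in the same list.
- Section 14.1, in the primary endpoint text, refers to patients who come off study "because of toxicity, death, or withdrawal of consent prior to undergoing a response assessment", again naming toxicity and consent withdrawal as different reasons.

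The synopsis allows dose reductions for patients who benefit but tolerate the drug poorly, and Section 9.2.2 (Tables 1 and 2) sets the levels and triggers. The synopsis text on secondary endpoints describes tolerability more broadly than item 5, as a summary of safety data over all cycles. Section 17.1 plans a tabulation of adverse events by severity and causality.

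**The concern.** Tolerability of a chronically dosed drug is about whether patients can stay on it at the intended dose. Item 5 counts one way of failing to do so. It requires that the patient, not the investigator, ends treatment, that the form is consent withdrawal, and that the cause is chronic toxicity of grade 1 or 2. Any other toxicity-driven stop counts as if the patient had tolerated the drug, and so does any dose reduction.

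The measure can also move the wrong way. As toxicity becomes more severe, patients are more likely to leave under Section 9.2 or 13.0, or to withdraw consent for grade 3-4 events. Either shift lowers the item 5 proportion.

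This matters because the rationale text just before Section 3.5 records that the schedule was changed after impaired tolerance, mainly fatigue, in the first two patients. A reader would look to the figure labelled tolerability to judge whether the revised schedule solved that problem, and it could be near zero while patients were stopping or reducing for toxicity.

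**Working it through.** **The plan's own figures.** The documents state no tolerability rate, target or threshold, so there is none to reproduce. The maximum denominator is the design's 20 patients. The stated two-stage rule (stop at 0/13, promising at 3 or more of 20, response rates 5% and 25%) reproduces as the minimax design with attained type I error 0.0736 and power 0.903. It confirms the denominator and has no other bearing on this point.

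**Step 1: what each planned analysis counts.**

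| Outcome for the patient | Item 5 tolerability | Item 5 safety / Section 17.1 tables |
|---|---|---|
| Withdraws consent, chronic grade 1/2 toxicity | Counted | Event only |
| Withdraws consent, grade 3-4 toxicity | Not counted | Event only |
| Off treatment, drug-related delay over 21 days (9.2) | Not counted | Event only |
| Removed by investigator for toxicity (13.0) | Not counted | Event only |
| Dose level reduced for toxicity (9.2.2) | Not counted | Event only |

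Neither the synopsis nor Sections 14.1, 16.1 and 17.1 name a proportion of patients who stopped or reduced treatment because of toxicity.

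**Step 2: interval formula.** For x of n, the exact (Clopper-Pearson) 95% limits are the 0.025 quantile of Beta(x, n−x+1) and the 0.975 quantile of Beta(x+1, n−x). For x = 0 the lower limit is 0 and the upper limit is 1 − 0.025^(1/n). With n = 20 that is 16.8%.

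**Step 3: missed discontinuations (assumed counts).** Suppose nobody withdraws consent for low-grade toxicity and x of 20 stop for toxicity by other routes. Item 5 then reports 0/20 = 0% (0-16.8%) whatever x is.

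| x | Toxicity discontinuation | Exact 95% CI |
|---|---|---|
| 2 | 10% | 1.2-31.7% |
| 4 | 20% | 5.7-43.7% |
| 8 | 40% | 19.1-63.9% |

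**Step 4: direction (assumed counts).** Suppose 3 of 20 withdraw consent for grade 2 toxicity. Item 5 gives 3/20 = 15% (3.2-37.9%). If one of the three instead worsens and is removed by the investigator, item 5 gives 2/20 = 10% (1.2-31.7%). Toxicity discontinuation is 3/20 in both cases. The direction follows from the definition and needs no assumed rate.

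**Step 5: missed dose reductions (from the documents).** The phase 1 safety data in Section 3 tabulate selinexor-attributed events in an AML cohort of n = 16, with each patient counted once per event at the highest grade. Events for which Table 2 states a dose-level reduction without a further condition are:

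- grade 3 headache 2, hypotension 1, AST increase 1 (row for other related events, grade 3);
- grade 4 neutropenia 1 (reduced with or without fever).

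The total is 2 + 1 + 1 + 1 = 5 patient-events. The two headache patients are distinct and the rest may overlap with them, so between 2 and 5 patients are involved: 2/16 = 12.5% (1.6-38.3%) to 5/16 = 31.3% (11.0-58.7%). Grade 3 fatigue, nausea and hypokalemia and grade 4 platelet decrease are left out because Table 2 or Section 9.2.5 makes reduction conditional or exempts the event. Scaled to this trial, 20 × 2/16 = 2.5 and 20 × 5/16 = 6.25, or about 2 to 6 patients. Item 5's tolerability figure would count none of these reductions.

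**The case against.** The strongest defence is that item 5 pairs two measures on purpose. Expected toxicity is mostly low grade: in the AML cohort, fatigue was grade 1-2 in 6 patients and grade 3 in 2, nausea 8 and 1, anorexia 7 and 0. A measure of attrition from persistent low-grade toxicity is therefore sensible, while more severe toxicity is picked up by the safety proportion and the Section 17.1 tables. The split by dose at onset also shows indirectly that some patients had been reduced, and the synopsis describes tolerability more widely. Toxicity exits before a response assessment already count as failures in the primary analysis. On this view a reader of the whole report would not be misled.

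Part of this stands. Low-grade attrition is worth reporting, and the toxic events themselves are not hidden. But those tables count events, not stopping or reducing treatment. The split by dose shows only patients who have a further event at the lower dose. The failure rule in the primary analysis concerns efficacy and ends at the first response assessment, so it says nothing about chronic dosing. The broader synopsis wording names no measure and does not match item 5, which is a reason to reconcile the two.

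Two points limit the size estimate. Table 2 is offered as guidelines, with modifications made in consultation with the Principal Investigator. Its row for other related events also carries a footnote mark whose note is absent from the available text, and four of the five events in Step 5 rest on that row. The AML range is an illustration.

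On cost, Section 16.1 does not name dose modifications among the database fields, so some abstraction from records may be needed.

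**Conclusion.** The concern holds. Followed as written, item 5 leaves every toxicity discontinuation other than low-grade consent withdrawal, and every dose reduction, out of the only figure defined as tolerability. That figure can fall as toxicity worsens. Both conclusions rest on the wording alone.

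The size cannot be fixed from the documents. The discontinuation scenarios are assumptions. The estimate of about 2 to 6 reduced patients assumes that rates from an AML cohort with a different disease, dose and schedule carry over, and that Table 2 is applied as stated.

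The endpoint is descriptive with no threshold attached, so sample size, error rates and the primary decision are untouched. The item should be amended because it answers a stated secondary objective incompletely and the remedy is cheap.

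**What to change.** Amend Section 14.1 item 5 to report, among patients who received at least one dose and with exact 95% confidence intervals:

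- (a) the proportion who permanently discontinue for selinexor-related toxicity of any grade and by any route, with the routes listed and consent withdrawal for grade 1/2 toxicity kept as one of them;
- (b) the proportion with at least one dose-level reduction for selinexor-related toxicity.

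Then align the synopsis text on secondary endpoints and the safety paragraph of Section 17.1 with the amended item. No clinical rule, visit or patient number changes.

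The cost is mainly wording. Section 9.2 already requires that "Each dose modification or treatment delay must be documented, including the respective reason", Section 13.0 puts the reason for withdrawal on the case report form, and Section 16.1 captures off-study documentation with toxicity grade and attribution. Item 5 already needs the dose at each toxicity, so dose data must be available. If reasons for dose changes are not in the database, they would have to be abstracted for at most 20 patients. The downside for the trial is that reported tolerability may look less favourable.
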